### 2.2 Endpoints

#### Primary endpoint

- Change in HPWSQ-R total score from Visit 2/Baseline to Visit 4

#### Secondary endpoints

1. Clinical Global Impression-Improvement after treatment (CGI-I) score at Day 8 and Visit 4
2. Change from Visit 2/Baseline to Day 8 and Visit 4 for the following measurements:
  - HPWSQ-R hyperphagia behavior, drive, and severity domain scores
  - HPWSQ-R-C total score
  - HPWSQ-R-C hyperphagia behavior, drive, and severity domain scores
3. Change from Visit 1/Baseline to Day 8 and Visit 4 for the following measurements:

- CY-BOCS score
- Food Domain of the Reiss Profile

4. Population PK/PD relationships for carbetocin

### **Safety endpoints**

- Frequency, severity and seriousness of adverse events
- Clinically significant changes in vital signs
- Clinically significant findings during physical and laboratory assessments
- Physical examinations, including focused nasal examinations and nasal irritation, graded according to the following scale:

Grade 0 = no abnormal findings

Grade 1A = focal nasal mucosal inflammation, erythema, or hyperemia

Grade 1B = superficial nasal mucosal erosion

Grade 2 = moderate nasal mucosal erosion

Grade 3 = nasal mucosal ulceration

Grade 4 = nasal septum perforation

### 3 Trial design

#### 3.1 General Design Considerations

This is a prospective, randomized, double-blind, placebo-controlled, multi-center, parallel trial in subjects with PWS between 10 and 18 years of age with genetically confirmed diagnosis of PWS and a documented nutritional phase 3 based on the criteria defined by Miller et al 2011. The trial includes a Screening Period, a 14-day Treatment Period, and a Follow-Up Period. Subjects, along with their parent or caregiver, will be required to visit the investigational site 4 times over the course of the trial, and participate in 2 phone call assessments.

- Visit 1: Screening Period (Day -7 to Day 0)
- Visit 2: Baseline 1st day dosing on site (Day 1)
- Visit 3: 2nd day dosing on site (Day 2)
- Phone call assessment (Day 8)
- Visit 4: End-of-Treatment Visit (Day 15)
- Follow-up phone call (Day 19±3)

Following appropriate informed consent procedures, subjects will undergo screening evaluations to determine eligibility before randomization. Screening evaluations include a physical examination, vital signs, height, weight, 12-lead electrocardiogram (ECG), nasal examination, and laboratory assessments - hematology, clinical chemistry, hemostasis, and urinalysis. Approximately 38 eligible male or female subjects will be randomized at Visit 2 to 1 of 2 treatment groups for 14 days:

- Carbetocin: each spray pump actuation will deliver a 50 µL volume of solution containing 1.6 mg carbetocin; each dose will consist of 3 spray pump actuations in each nostril to deliver a total of 9.6 mg carbetocin
- Placebo: each spray pump actuation will deliver a 50 µL volume of sterile sodium chloride solution 0.9%; each dose will consist of 3 spray pump actuations in each nostril

After randomization, efficacy measures and other assessments, including physical examination, vital signs, nasal examination, and collection of blood samples for clinical laboratory and pharmacokinetic (PK) evaluation, will be performed at selected visits according to Schedule of Activities in the Protocol. Subjects will be closely monitored for adverse events throughout the trial following informed consent.

Prior to first dosing at the investigational site, parents/caregivers will be trained on the proper use of the nasal spray device and procedures for Investigational Medicinal Product (IMP) home delivery. Parents/caregivers will be instructed to administer 3 intranasal spray pumps of blinded IMP per nostril 3 times daily before meals within the following intervals:

Morning dose: 06:00 a.m. – 09:00 a.m.

Midday dose: 11:00 a.m. – 1:00 p.m.

Evening dose: 4:30 p.m. – 6:00 p.m.

Initial IMP dosing at Visit 2 (Day 1) and Visit 3 (Day 2) will take place under observation of the site staff at the investigational site. Subject vital signs will be monitored prior to and after IMP dosing at 30-minute intervals for 2 hours after each dose. IMP will be shipped by central pharmacy directly to the subject's residence on regular intervals as needed for the duration of the Treatment Period. IMP will be administered by parents/caregivers 3 times per day before meals within the above specified dosing intervals. The IMP will require refrigeration during shipment to and during storage at the investigational site or subject's residence until administered.

### **3.2 Determination of Sample Size**

Based on available literature (Dykens et al 2007), the HPWSQ-R total score at baseline (Visit 2) is assumed to be normally distributed with a standard deviation of 6.12, and the standard deviation of the change between baseline (Visit 2) and Visit 4 is estimated to be between 5 and 6. With 30 subjects eligible for the primary efficacy assessment, the trial has at least 80% power to detect a borderline statistically significant difference (1-sided 10% significance) between 2 groups when the true treatment group difference is -5 under the standard deviation of 5 to 6. Subjects are randomized in a 1:1 ratio to either placebo or carbetocin.

The efficacy of carbetocin will be assessed by change in HPWSQ-R total score from Visit 2/Baseline to Visit 4. Assuming a dropout rate of approximately 20%, at least 19 subjects per treatment arm will need to be randomized to have a total of 30 subjects eligible for the primary efficacy assessment.

#### **4 Subject Disposition**

The number of subjects who enrolled and/or randomized into the trial will be summarized overall. Subjects who discontinue IMP or are removed from the trial permanently will also be reported by the treatment received immediately prior to discontinuation. Reasons for trial discontinuation will be summarized by treatment as well as randomization errors and time of withdrawal from the trial, if appropriate. No formal statistical analysis will be performed.

The number of subjects screened but not randomized/allocated to treatment will be presented with the reason(s) for screen failure in a data listing.

## 5 Protocol Deviations

Rating of protocol deviations as ‘minor’ and ‘major’ will be decided by the Ferring clinical team on the basis of a blinded review of data before declaration of clean file and lock of database. Major protocol deviations will lead to exclusion of data from the Per Protocol analyses. Minor protocol deviations will not lead to exclusion of data from any analyses.

The full list of major protocol deviations will be detailed and documented in the clean file document prior to treatment unblinding.

Major protocol deviations include, but are not restricted to, the following:

- Violation of inclusion or exclusion criteria that may affect the efficacy analysis such as:
  - Inclusion criterion 4, genetically confirmed diagnosis of PWS
  - Inclusion criterion 5, Nutritional phase 3 PWS criteria based on Miller et al, 2011;
  - Inclusion criterion 6, HPWSQ-R score greater than 13 at screening, Visit 1
  - Exclusion criterion 5, Prior or concomitant use of a selective serotonin reuptake inhibitor (SSRI) or selective norepinephrine reuptake inhibitor (SNRI), antipsychotic medication, wakefulness-promoting drug, or thyroid hormone that does not comply with the criteria in Section 4.3.1 of the Protocol;
  - Exclusion criterion 6, Use of any of the prohibited medications or therapies listed in Section 4.3.2 of Protocol
- Actual treatment not in accordance with randomized treatment.
- Less 80% compliance with treatment and/or missing more than 4 consecutive doses
- HPWSQ-R assessment not completed on Day 15

## 6 Analysis sets

### 6.1 Intention-To-Treat Analysis Set

The intention-to-treat (ITT) analysis set comprises of all randomized (as planned) subjects.

### 6.2 Full-Analysis Set

The full analysis set (FAS) population will include all subjects in the safety population who have the primary efficacy endpoint measured (Baseline and Day 8±1 or Day 15). Analyses for the FAS will be conducted according to the randomized treatment. The primary endpoint will be analyzed in the FAS population.

### 6.3 Per Protocol Analysis Set

Subjects in the FAS population with major protocol deviations will be excluded from the PP (per-protocol) analysis set. These subjects will be identified prior to breaking the study blind. Analyses for the PP will be conducted according to the randomized treatment.

### 6.4 Safety Analysis Set

All subjects who received any amount of IMP will be included in the safety population. Analyses for the safety population will be conducted according to the actual treatment received.

### 6.5 Pharmacokinetic Analysis Set

The pharmacokinetic (PK) population will include all subjects in the safety population who have sufficient plasma carbetocin concentrations for inclusion in population PK modeling. *PK analysis will be addressed in a separate document.*

## 7 Trial population

### 7.1 Demographics and Other Baseline Characteristics

Categorical data will be summarized using numbers and percentages. The percentages are based on the total number of subjects with a corresponding assessment. Continuous data will be presented, for example, using the number of subjects (n), mean and standard deviation, median, minimum and maximum. Summary will be conducted for the safety population or FAS population if specified. All baseline characteristics will be listed.

Missing values concerning demographics and baseline characteristics will not be imputed.

#### 7.1.1 Demographics

Baseline demographics variables include age, sex, race and ethnicity, height, weight and Body Mass Index (BMI). Age will be calculated as (Date of Informed Consent – Date of Birth)/365.25, rounded down to the nearest integer. BMI will be calculated as body weight (kg)/(height (m)), rounded to one decimal place.

Descriptive statistics of the demographics variables will be summarized based on FAS population by treatment randomized as well as based on safety population by actual treatment. No formal statistical analysis will be performed.

#### 7.1.2 Vital Signs at Baseline

Baseline vital signs (blood pressure, pulse, body temperature, and respiration rate) will be summarized by treatment.

#### 7.1.3 Trial-specific Baseline Variables or History of Disease

Descriptive statistics will be summarized by treatment for urine drug screen and alcohol test, and nutritional phase assessment.

Other baseline assessments will be presented and summarized in by-visit tables or in listings.

#### 7.1.4 Laboratory Efficacy/Pharmacodynamic Parameters at Baseline

PK analysis will be addressed in a separate document.

## 7.2 Medical History

Medical and surgical history recorded at screening visit will be coded using Medical Dictionary for Regulatory Activities (MedDRA) version 16.1. Medical and surgical history will be listed by treatment and subject as well as summarized by system organ class (SOC) and preferred term (PT).

### **7.3 Prior and Concomitant Medication**

Prior and concomitant medications will be coded using World Health Organisation Drug (WHODrug) Dictionary version 01SEP2013. Medications will be listed by treatment and subject as well as summarized by Anatomical Therapeutic Chemical (ATC) classification 1st level (alphabetically), ATC classification 2nd level (in decreasing order of frequency) and treatment group. These medications will be tabulated separately for:

- 1) Prior medication; i.e. medication taken exclusively prior to first IMP administration
- 2) Concomitant medication, i.e. medication taken after IMP administration

If the timing of the dose of a concomitant medication cannot be established in relation to the administration of IMP, it will be considered as concomitant medication.

### **7.4 Physical Examination**

Physical examination results will be listed by treatment and subject. Subjects with abnormalities at any screening, baseline, or post-baseline visit will be listed with all physical examination evaluations by body system for the Safety analysis set.

## **8 Exposure and Treatment Compliance**

### **8.1.1 Extent of Exposure**

The total trial treatment exposure will be summarized by treatment group for the safety population. Summary statistics are provided for the duration of exposure (number of days) of study medication (last known date patient took study medication - first dose date + 1).

### **8.1.2 Treatment Compliance**

Treatment administration collected in the clinical report form (CRF) will be listed by treatment and subject. Treatment compliance will be calculated as (the number of actual doses intake / the number of planned doses)\*100% where an actual dose consists of a total of six sprays between the two nostrils. The number of planned doses is 42 (=14\*3) per study design.

The number of subjects who had at least 80% treatment compliance and missed no more than 4 consecutive dosing time-points will be summarized. The calculated treatment compliance will be listed as well.

## 9 Efficacy

### 9.1 General Considerations

Efficacy analysis will be conducted for the FAS population unless otherwise specified. All statistical tests will be performed using a one-sided test at a 10% significance level. No adjustments will be made for multiple tests. Baseline for all efficacy analyses will be the values obtained at the last assessment prior to the first dose of IMP.

#### Handling of missing scores of questionnaire

A subscore or domain score of the HPWSQ-R questionnaire is defined as the sum of all items scores in the domain. The average value of completed items in a domain will be used as an estimate of missing items. If more than 50 percent of the items from a domain are missing, the corresponding domain score will be set to missing. Total score is the sum of these three subscores. Total score will be missing if any subscore is missing.

The last observation carried forward (LOCF) method will be used to carry forward non-missing values of HPWSQ-R total score during the phone call assessment (Day 8±1) to impute missing values of HPWSQ-R total score at Visit 4 (i.e. exactly on Day 15). Any assessments not within the window Day 8±1 and prior to Day 15 will not be used for LOCF imputation. For subjects who discontinued IMP prior to Day 12, if they have HPWSQ-R assessments on Day 15, then the assessments are considered invalid for primary endpoint analysis. LOCF values at Day 15 will be populated with non-missing values of HPWSQ-R total score during the phone call assessment (Day 8±1).

Similarly, HPWSQ-R-C will be handled in the same way as HPWSQ-R. The analyses of HPWSQ-R and HPWSQ-R-C will be conducted based on LOCF values unless otherwise specified.

No imputation will be applied to the domain score of HPWSQ-R and HPWSQ-R-C, and other questionnaires (Clinical Global Impression, CY-BOCS and Food Domain of the Reiss Profile).

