### **3.1.2 Trial Schedule**

For each subject, there will be a Screening period and a 14-day Treatment period. An End-of-Treatment Visit will be conducted on Day 15 and a Follow-up phone call will be conducted 4 days ( $\pm 3$  days) after the End-of-Treatment Visit.

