### **3.5 Discussion of Overall Trial Design and Choice of Control Groups**

#### **3.5.1 Trial Design**

Placebo is a standard control used to ensure unbiased estimates for the effects of active treatment. The 14-day duration of treatment was considered sufficient to observe the onset of efficacy for an active treatment of PWS.

Since PWS is a rare condition, and subjects with PWS are generally treated at a few centers of excellence throughout the country, it is expected that a significant proportion of eligible subjects will reside at a considerable geographic distance from the investigational site(s), requiring ground or air transportation to complete trial visits. The trial design considers both the geographic challenges, as well as the need to ensure subjects' home-life "normalcy" during the trial in order to accurately assess treatment effect.

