### **9.2.2 Sensitivity Analyses**

The analysis of the primary endpoint in the section 9.2.1 will be also conducted based on the subjects in the PP population and ITT population.

In addition, the primary endpoint will be analyzed using repeated measures analysis with treatment, site, visit and treatment-by-visit interaction as fixed effects and HPWSQ-R total score at baseline as a covariate. An unstructured working correlation matrix will be used for the analysis. LOCF will not be used to impute missing values because it would affect the correlation of observations between weeks. The two treatment groups will be compared at Visit 4 (Day 15). The LS means, the LS mean difference, and 90% 1-sided confidence interval (CI) for the treatment difference will be presented will be presented at each visit as well.

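### SAP 9.1 counts a Visit 4 HPWSQ-R only if rated exactly on Day 15, so a rating a day or two off is replaced by the Day 8±1 phone score, which describes almost entirely a different week

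*Combined protocol and SAP*

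**What the plan says.** Protocol section 3.1.2 fixes the last visit to a single day: "An End-of-Treatment Visit will be conducted on Day 15". Table 1 gives the phone assessment ±1 day and the follow-up call ±3 days, but gives Visit 4 no tolerance.

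SAP section 9.1 (handling of missing questionnaire scores) turns that schedule into an analysis rule with three parts:

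- The phone score from Day 8±1 serves to "impute missing values of HPWSQ-R total score at Visit 4 (i.e. exactly on Day 15"), which gives Visit 4 a width of zero.
- A second sentence limits the source of the carried value: "Any assessments not within the window Day 8±1 and prior to Day 15 will not be used for LOCF imputation". This shuts out ratings made on Days 10 to 14.
- Early stopping of treatment has its own rule. It opens "For subjects who discontinued IMP prior to Day 12, if they have HPWSQ-R assessments on Day 15", and goes on to set those ratings aside in favour of the phone score.

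Other SAP sections follow the same day. Section 6.2 puts in the FAS treated subjects "who have the primary efficacy endpoint measured (Baseline and Day 8±1 or Day 15"). Section 5 lists as a major deviation "HPWSQ-R assessment not completed on Day 15", which removes the subject from the per-protocol set. Section 9.2.1 names the primary variable by visit, with Day 15 in brackets. Section 9.2.2 repeats that analysis in the per-protocol and ITT sets and adds a repeated-measures model, for which "LOCF will not be used to impute missing values because it would affect the correlation of observations between weeks". HPWSQ-R-C total scores are handled in the same way as HPWSQ-R.

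**The concern.** An off-day Visit 4 is already a departure from the schedule. The question is what becomes of its score. The exact-day wording sets aside a rating made close to the target day and puts in its place one made about a week earlier, by telephone, halfway through treatment.

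Such visits can be expected to occur. Protocol section 3.5.1 foresees that many subjects will live far from a site, "requiring ground or air transportation to complete trial visits". Section 3.5.6 has withdrawing subjects advised to agree to the Visit 4 procedures, which would then usually fall on another day.

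At stake is the primary estimate. If the effect at Day 8 is smaller than at Day 15, each substitution in the carbetocin arm pulls the estimated difference toward zero. A subject with an off-day rating and no Day 8±1 score leaves the FAS, and every subject without a Day 15 rating leaves the per-protocol set. The trial plans on only 30 evaluable subjects.

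**Working it through.** **1. The rule by day of rating**

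| Day of HPWSQ-R | Treatment under SAP 9.1 |
|---|---|
| 7 to 9 | May be carried forward |
| 10 to 14 | Neither the Visit 4 value nor a permitted LOCF source |
| 15 | Visit 4 value, unless IMP stopped before Day 12 |
| 16 or later | Not exactly Day 15, so read literally Visit 4 is missing and Day 8±1 is carried forward |

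The ITT rerun inherits this. SAP 9.2.2 repeats the 9.2.1 analysis, 9.2 refers missing scores to 9.1, and 9.1 applies LOCF values unless stated otherwise. Only the repeated-measures model has no rule for assigning an off-day score, although it makes no Day 8 substitution.

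One consequence is odd. A subject whose last dose was on Day 12 and who is rated on Day 15 is kept. A fully dosed subject rated on Day 14 has that rating replaced by one about six days older.

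**2. Recall overlap**

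Protocol section 3.5.2 gives a one-week recall. Assume that a rating on day d covers days d−7 to d−1, so that Day 15 covers Days 8 to 14. Overlap = max(0, 7 − |15 − d|).

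- d = 14 or 16: 7 − 1 = 6 days
- d = 13 or 17: 7 − 2 = 5 days
- d = 9: 7 − 6 = 1 day
- d = 7 or 8: 0 days

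Counting the rating day itself shifts every week by one day and leaves the overlaps unchanged.

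**3. The plan's own power figure**

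Inputs from SAP 3.2: 15 evaluable per arm, difference −5, SD of change 5 to 6, one-sided 10%. For the unadjusted t-test, SE = SD × √(2/15), noncentrality = 5/SE, 28 df.

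- SD 6: SE 2.19, noncentrality 2.28, power 83.3%
- SD 5: SE 1.83, noncentrality 2.74, power 92.2%

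The stated minimum of 80% is reproduced.

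**4. Planned ANCOVA with none replaced**

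The baseline SD is 6.12 (SAP 3.2). Assume equal variances across visits and three sites.

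- ρ = 1 − SD²/(2 × 6.12²). At SD 6 this is 1 − 36/74.91 = 0.519.
- Residual SD = 6.12 × √(1 − 0.519²) = 5.23.
- df = 30 − 5 = 25. SE = 5.23 × √(2/15) = 1.91, noncentrality 2.62, power 90.2%.

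**5. Effect of replacement (illustration)**

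Let f be the share of subjects replaced, the same in each arm, and r the Day 8 effect as a fraction of the Day 15 effect. Neither is in the documents. Expected estimate = −5 × [1 − f(1 − r)].

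| f | r | Expected estimate | Closed-form ANCOVA power, SD 6 | Simulated ANCOVA power, SD 6 |
|---|---|---|---|---|
| 0 | – | −5.00 | 90.2% | about 89.5% |
| 1/30 | 0.5 | −4.92 | 89.4% | – |
| 0.20 | 0.5 | −4.50 | 85.0% | about 83.5% |
| 0.20 | 0 | −4.00 | 78.2% | about 75% |

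The simulation replaces 3 of 15 per arm and takes equal correlations between visits. It is the better guide. The closed form holds the SD fixed, whereas mixing Day 8 and Day 15 effects within the carbetocin arm adds spread. At SD 5 the closed form runs from 95.2% (none replaced) to 86.0% (f = 0.20, r = 0). With r = 1 the expected estimate stays at −5.00 for any f.

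**The case against.** **The SAP follows the schedule.** The protocol sets Visit 4 on Day 15 without tolerance, and SAP 5, 6.2, 9.1 and 9.2.1 all use that day. The exact-day wording also does useful work: it stops, for example, a Day 5 early-termination rating from being labelled Visit 4. This stands, and a reader who infers that the SAP leaves Visit 4 without any rule would be wrong. The rule exists and has zero width. A short window would still exclude early terminations of that kind.

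**A Day 16 or 17 rating.** A reader might infer that its handling is undefined, because the bar on carrying forward reaches only scores before Day 15. The documents do not support that. A later score could not be carried forward to Day 15 in any case, and the word exactly makes Day 15 missing. What remains is a small opening: SAP 9.2.1 names the endpoint by visit, and someone working from that could keep the score.

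**Few subjects are affected.** Protocol 3.5.1 says that the design takes geography into account, and 3.5.6 only advises withdrawing subjects to agree to the Visit 4 procedures, as safety follow-up. Both points stand. The group is visits a day or two off schedule, plus early terminations on Days 13 to 14 in subjects who stopped IMP on Day 12 or later. No passage supports a 10% or 20% rate.

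**An off-day rating is not equivalent to a Day 15 rating.** A Day 13 or 14 rating precedes the end of the 14-day course, and a Day 16 or 17 rating takes in drug-free days. This is a fair cost of any window. It does not make the Day 8±1 score the nearer substitute.

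**Conclusion.** The point holds as a minor one. In the primary analysis and the ITT rerun, a Day 13 or 14 HPWSQ-R gives way to a score whose recall week shares at most 1 of the 7 target days, although the discarded rating shares 5 or 6. Read literally, the same happens to a Day 16 or 17 rating. No other section restores the discarded rating to the primary analysis.

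The direction of the effect depends on an unproven premise, that the treatment effect is smaller at Day 8 than at Day 15. If the two are equal, nothing is lost. The size is unknown. At SD 6 the 20% illustrations cost about 6 points of simulated power (89.5 − 83.5) or about 14 to 15 points (89.5 − 75). A likelier case, about 1 of 30 replaced with a half-size Day 8 effect, costs under 1 point (90.2 − 89.4 = 0.8).

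Two stronger readings should be resisted. The first is that the trial is underpowered. Under the planned ANCOVA, only the extreme with 20% replaced, no Day 8 effect and SD 6 falls below 80%. The second is that the rule could produce a false positive. It is pre-specified and does not depend on arm, so no such risk arises. The overlap figures assume that recall means the seven days around the rating as set out above. The power figures also assume equal visit variances and three sites.

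**What to change.** Before unblinding, amend SAP 9.1 as follows:

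- Define a short Visit 4 analysis window around Day 15, for example ±1 or ±2 days. The width is a judgement that the documents do not settle.
- Use the HPWSQ-R closest to Day 15, with a stated tie rule such as taking the earlier rating.
- Apply the existing Day 12 discontinuation rule to any score in the window, and keep Day 8±1 LOCF when no score falls in it.
- Align the major-deviation item in SAP 5 and the FAS definition in 6.2, and apply the window to HPWSQ-R-C and the repeated-measures model.
- Keep the exact-Day-15 rule as a sensitivity analysis.

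At minimum, leave the primary rule as it is, add the windowed analysis as a sensitivity analysis, and state in one sentence how a rating after Day 15 is handled.

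The cost is SAP wording and a little programming, with no new data and no change to the visit schedule. The downside is a slightly shifted recall week. In a subject dosed through Day 14, a Day 16 rating includes one drug-free day (Day 15) and a Day 17 rating two (Days 15 and 16). The SAP already accepts two, for a last dose on Day 12 and a rating on Day 15 (Days 13 and 14). With a last dose on Day 12, a Day 16 rating would include three (Days 13 to 15) and a Day 17 rating four (Days 13 to 16), which is an argument for the narrower window.

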### **9.6 Endpoint Assessments**

#### **9.6.1 Efficacy Analyses**

The primary endpoint will be analyzed in the FAS population using an analysis of covariance (ANCOVA) model with treatment and site as fixed effects and HPWSQ-R (completed by the parent/caregiver) total score at Visit 2 (baseline) as a covariate. The last observation carried forward (LOCF) method will be used to carry forward non-missing values of HPWSQ-R total score during the phone call assessment (Day 8±1) to impute missing values of HPWSQ-R total score at Visit 4. The treatment group difference in total score between placebo and carbetocin will be calculated by subtracting the mean change from baseline in placebo from that in the carbetocin group. A borderline statistically significant difference at the 10% significant level will be achieved if the upper limit of the 90% 1-sided confidence interval for the treatment difference is less than zero.

The secondary endpoints will be analyzed using a similar model to that of the primary endpoint.

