## 1 Introduction

This Statistical Analysis Plan (SAP) describes the planned statistical analyses for Trial 000114 based on the protocol amendment (version 4, dated 10 February 2014) “A Prospective, Randomized, Double-Blind, Placebo-Controlled Study to Evaluate the Safety and Effectiveness of Intranasal Carbetocin in Subjects with Prader Willi Syndrome (PWS)”.

The SAP provides a more technical and detailed elaboration of the statistical analyses of efficacy and safety as outlined and/or specified in the protocol as well as data handling rules and exploratory analyses not mentioned in the protocol.

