## **12 Deviations from protocol analysis**

There are no deviations from the analyses planned in the protocol.

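### SAP 9.1 sets aside observed Day 15 HPWSQ-R totals after an early stop of IMP and inserts Day 8 scores; the protocol imputes only missing totals, SAP 12 declares no deviation, and no planned analysis of the total clearly tests the rule

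*Combined protocol and SAP*

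**What the plan says.** Protocol 9.6.1, and the synopsis in the same terms, use last observation carried forward from the Day 8±1 phone call "to impute missing values of HPWSQ-R total score at Visit 4". Neither gives a rule for a Visit 4 total that was observed after IMP had been stopped.

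SAP 9.1 (handling of missing questionnaire scores) repeats that rule, defines Visit 4 as exactly Day 15, and adds a second rule. For subjects who discontinued IMP before Day 12, "if they have HPWSQ-R assessments on Day 15, then the assessments are considered invalid for primary endpoint analysis". The Day 15 value is then filled from the Day 8±1 call. The HPWSQ-R-C total is treated likewise. The default for both scales is that "The analyses of HPWSQ-R and HPWSQ-R-C will be conducted based on LOCF values unless otherwise specified". Domain scores are not imputed.

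SAP 12 states: "There are no deviations from the analyses planned in the protocol". SAP 1 describes the SAP as also covering "data handling rules and exploratory analyses not mentioned in the protocol".

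Three other places bear on the point:
- SAP 6.2 admits to the FAS treated subjects "who have the primary efficacy endpoint measured (Baseline and Day 8±1 or Day 15").
- SAP 5 lists as a major deviation "Less 80% compliance with treatment and/or missing more than 4 consecutive doses", and SAP 6.3 adds that "Subjects in the FAS population with major protocol deviations will be excluded from the PP (per-protocol) analysis set".
- SAP 9.2.2 repeats the primary analysis in the PP and ITT sets and adds a repeated measures model without LOCF.

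**The concern.** An observed score is not a missing score. The SAP rule replaces primary endpoint values that the protocol's imputation rule leaves alone. It moves the primary analysis from the Visit 4 outcome as observed towards an outcome partly confined to time on drug. That can be a legitimate target, but it is a different one, and the section of the SAP meant to record such changes says that there are none.

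Two things are at stake. First, the record of what was planned is inaccurate for the primary analysis. Second, relative to the protocol's Visit 4 comparison, the estimate could shift if early stopping, or the Day 8 to Day 15 change among those who stop, differs between arms. The trial is judged on a single one-sided 90% confidence limit in about 30 subjects, so a few substituted values could be visible. The planned sensitivity analyses should show whether they are, and as written they do not clearly do so.

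**Working it through.** **1. The two rules side by side.** Take a subject with a baseline, a Day 8 and a Day 15 total who stopped IMP before Day 12. Under protocol 9.6.1 the Visit 4 total is present, nothing is imputed and the Day 15 total is analysed. Under SAP 9.1 the Day 15 total is set aside and the Day 8 total is analysed. The same subject contributes different data, so this is more than a detail of one rule.

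**2. Does the PP run test it?** SAP 8.1.2 gives 14 × 3 = 42 planned doses, which reproduces. Taking stopping before Day 12 to mean a last dose on Day 11 at the latest:
- doses received ≤ 11 × 3 = 33
- compliance ≤ 33/42 = 78.6%, below 80%
- consecutive doses missed at the end ≥ 42 − 33 = 9, more than 4

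Every affected subject is a major deviator under SAP 5 and is out of the PP set. The PP run cannot test the substitution.

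**3. Do the other runs test it?**
- ITT: repeats the SAP 9.2.1 analysis, by default on LOCF values, so the substituted scores stay in.
- Repeated measures: no LOCF, but SAP 9.2.2 does not say whether the invalidated Day 15 totals enter. If they do, the model tests the rule directly. If they do not, it shows only what happens without the Day 8 insertion.
- Domain scores: read literally, observed Day 15 domain scores stay in the secondary analyses. This is an indirect check, not one on the total.

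**4. What the substituted score measures.** The questionnaire has a 1-week recall (protocol 3.5.2). Assume that it covers the 7 days before each assessment, with the call on Day 8. On-drug days out of 7, for last dose on Day 1, 2, …, 11:
- Day 8 score: 1, 2, 3, 4, 5, 6, 7, 7, 7, 7, 7
- Day 15 score: 0, 0, 0, 0, 0, 0, 0, 1, 2, 3, 4

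The rule always picks the score with more on-drug days. After a very early stop (last dose Day 1 to 3), even that score has only 1 to 3 on-drug days. Hence partly on-treatment.

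**5. Possible size (assumed; the documents give no rate of affected subjects).** The design figures reproduce: with 15 per arm, difference −5 and one-sided 10% significance, power is 92.7% at SD 5 and 84.1% at SD 6 (normal approximation), against a stated minimum of 80%; 15/(1 − 0.20) = 18.75, so 19 per arm. The point changes none of these.

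Shift in the treatment difference = (k1 − k0) × d / 15, where k1 and k0 are the affected subjects in each arm and d is the Day 8 to Day 15 gap, taken as equal for all of them.
- d = 5; k1 = 1, 2, 3; k0 = 0: 0.33, 0.67, 1.00
- d = 2.5; same k: 0.17, 0.33, 0.50
- d = 5; 2 v 1: 0.33
- d = 5; 2 v 2: 0

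The sign of d is unknown, so each shift can go either way. A simulation of the ANCOVA with three sites and a baseline covariate gave average shifts within about 0.01 of these. For scale, the unadjusted standard error is SD × √(2/15) = 1.8 at SD 5 and 2.2 at SD 6, so the largest assumed shift is about half a standard error.

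**6. FAS membership.** A subject with baseline and Day 15 only who stopped before Day 12 meets the wording of SAP 6.2, has the Day 15 total invalidated, and has no Day 8 score to carry forward.

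**The case against.** The best defence is delegation. Protocol section 9 leaves statistical detail to the SAP, and SAP 1 claims data handling rules that the protocol does not mention. The protocol never says when a Visit 4 score is valid; the model, covariates, analysis population and source of the carried value are unchanged. On this view the Day 12 rule only defines a usable score. This does not fully answer the point. The protocol does state which Visit 4 totals are imputed, namely missing ones, and the SAP widens that set to include observed ones.

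The rest of the defence largely stands. The rule is pre-specified, applies to both arms and keeps subjects in their randomised arm. An on-treatment target is a reasonable choice in a 14-day phase 2a trial, and the recall-day counts suggest why the rule was written.

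The affected group may also be close to empty. A subject must stop before Day 12 and still be assessed exactly on Day 15, whereas protocol 3.5.6 asks withdrawing subjects to complete the Visit 4 procedures before leaving, and Table 1 uses the same column for early termination. The FAS gap is rarer still, and one could read an invalidated score as not measured, so that the subject never enters the FAS.

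A reader might infer that the analysed effect cannot be identified. The documents do not support that: SAP 9.1 states the trigger, the cut-off and the replacement value. A reader might also infer that the rule favours carbetocin or inflates the false-positive rate. Nothing in the documents gives the number of early stoppers, their split by arm or their change from Day 8 to Day 15, so neither a direction nor an error rate can be derived.

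**Conclusion.** The inconsistency holds on the text. SAP 9.1 replaces some observed primary endpoint values, the protocol imputes only missing ones, and the SAP 12 statement is therefore inaccurate. No planned analysis of the total clearly isolates the effect of the rule. It should be fixed, because this is the primary analysis and the remedy is cheap.

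The consequence is uncertain and may be nil. The range of 0.33 to 1.00 point rests on 15 per arm, 1 to 3 affected subjects all in one arm and a 5-point gap, which equals the whole design effect. Smaller gaps or a more even split shrink it, and an equal split with the same gap removes it.

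One might conclude that the observed Day 15 totals must be primary. That goes beyond the documents: which effect to target is partly the sponsor's choice. What follows from the inconsistency is that the choice be declared, justified and checked.

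**What to change.** Choose one of two routes.
- **Keep the rule as primary.** Correct SAP 12 so that it declares the rule and justifies it, including the Day 12 cut-off. Add a sensitivity ANCOVA that uses totals observed on Day 15 regardless of IMP discontinuation.
- **Restore the protocol rule as primary.** Analyse totals observed on Day 15 as randomised and apply LOCF only to totals that are truly missing. Keep the Day 12 rule as a labelled on-treatment sensitivity analysis.

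Under either route:
- state in SAP 9.2.2 that the repeated measures model uses the observed Day 15 totals
- state how early-termination Visit 4 scores taken before Day 15 are handled; SAP 9.1 excludes those taken outside the Day 8±1 window, while the protocol is silent
- apply the same decisions to the HPWSQ-R-C total
- align SAP 6.2 so that no FAS member lacks a usable primary value

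The cost is SAP wording and one extra run on data already planned for collection. Sample size and power are unchanged. The downside is that one of the two analyses includes some off-drug scores.
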